#### **4.3 Participant Recruitment**

Participants will be recruited at multiple centers around the U.S. Participants will be identified by reviewing clinic schedules each week and reviewing charts of likely eligible patients. Patients may be approached via telephone or when they come to the clinic for a clinical visit. Participants may agree to consent at the time of their clinic visit or may return to the clinic on another day to be consented. In some cases, a verbal consent via telephone may be done prior to an in-person visit where a full in-person consent process will be completed. Participants may also be recruited through CCFA Partners and referred to a participating clinic.

#### **4.4 Duration of Study Participation**

Participation in the study will last a minimum of 13 weeks from the time participants consent and are screened, for those who complete the study protocol. Adherence to the study diet will take place for up

to 12 weeks. Participation may last up to 16 weeks if the maximum time between screening and randomization is allowed.

#### **4.5 Total Number of Subjects and Sites**

It is expected that 230 participants will need to be enrolled (defined as having provided informed consent to participate in this research study) to achieve a final sample size of 194 participants. Recruitment will end when approximately 194 participants have been randomized.

#### **4.6 Vulnerable Populations**

Children, pregnant women, fetuses, neonates, or prisoners are not included in this research study.

### **5 Study Intervention**

#### **5.1 Description**

The study intervention is the Specific Carbohydrate diet (SCD). The study diet is based on the detailed descriptions of allowable food in the book *Breaking the Vicious Cycle*, by Elaine Gottschall. We will use this list of allowed foods to create the menu of food items for the participants randomized to receive the SCD. The SCD restricts all but simple carbohydrates. The only carbohydrates permitted are monosaccharides: glucose, fructose, and galactose. Fresh fruits and vegetables are universally acceptable with the exception of potatoes and yams. Certain legumes (i.e. lentils, split peas) are permitted, however others (i.e. chickpeas, soybeans) are not. No grains are permitted in the SCD. Saccharin and honey are permitted in addition to moderate use of sorbitol and xylitol. Canned fruits and vegetables are not permitted due to possible added sugars and starches. Unprocessed meats are permitted in the SCD without limitation. However processed, canned, and most smoked meats are restricted due to possible sugars and starches used in additives. Milk is not permitted in the SCD due to lactose content. However, certain lactose free cheeses are permitted as is homemade lactose-free yogurt.

The control diet is a Mediterranean Style Diet. This is a well-balanced diet that is consistent with the United States Department of Agriculture and World Health Organization recommendations. The MSD entails higher fiber intake and appreciably lower red meat intake than the average American diet. It involves a high intake of olive oil, fruit, nuts, vegetables, and cereals; a moderate intake of legumes, fish, seafood, and poultry; a low intake of dairy products, red meat, processed meats, and sweets; and wine in moderation, consumed with meals. Red and processed meats, soda drinks, bakery goods, sweets, pastries, and spreadable fats are not permitted on this diet. Wine is allowed only with meals and no more than two 5 oz. glasses per day.

#### **5.2 Intervention Regimen**

Participants will be provided with fully prepared meals from Healthy Chef Creations (HCC) totaling a minimum of 2500 calories. Participants do not have to eat all of the food provided. Beverages will not be provided, but participants will be provided with a list of recommended beverages. Participants will receive these meals for six weeks. Some of the meals will require heating.

During weeks 7 through 12 participants will be asked to adhere to their randomized diet by preparing their own meals and snacks or by purchasing the meals from HCC. Participants will be provided with detailed instructions and recipes for preparing their food.

#### **5.3 Receipt**

Participants will receive shipments of food to their home (or another location, if desired) each week via tracked courier from HCC. Shipments will occur on Fridays. These shipments will contain breakfast, lunch, dinner and two snacks for each day of the week. The food will be delivered fresh (not frozen) with sufficient ice packs to remain on a door step until later that evening. Each shipment will contain instructions on how to reheat the meal (if needed), whether or not the meal can be frozen and how long the meal can be kept under refrigeration before consumed. Additionally, each shipment will contain contact information for customer service representatives of HCC. The representatives can be contacted for any questions about the food, its ingredients, preparation instructions etc.

#### **5.4 Storage**

Each meal or snack will be labeled with the storage requirements for that meal (freeze, refrigerate, keep at room temperature). Proper preparation with regard to reheating will also be included on a label on each meal/snack.

#### **5.5 Preparation and Packaging**

All of the meals and snacks for this study will be prepared by HCC in a single kitchen. All participants, regardless of the clinical center from which they were recruited, will receive their meals from HCC directly to their homes via tracked courier. Food will arrive in a cardboard box with the food inside surrounded by freezer packs. The box will have a label reading "Perishable."

#### **5.6 Administration and Accountability**

HCC will provide a monthly report detailing all of the food deliveries including the date they were delivered and to whom. This report will include information on whether additional meals needed to be delivered to replace damaged shipments or shipments not received.

#### **5.7 Subject Compliance Monitoring**

Adherence to the assigned diet will be assessed using three 24-hour dietary recalls administered by trained dietitians on randomly selected days. This assessment will occur once between screening and start of study diet, once during week 6 and once during week 12. We will also have participants complete a diet history questionnaire (DHQ) at baseline and week 12. The DHQ asks about food eaten in the past 30 days. Therefore, the week 12 DHQ will be used in addition to the 24 hour dietary recall to assess adherence to the assigned diet.

##### **5.7.1 Return or Destruction of Investigational Product**

Participants will be allowed to keep all meals that are delivered to their homes. If meals are past their expiration date or if they are unwanted by the participant, the participant will be responsible for disposing of the meals.

### **6 Study Procedures**

#### **6.1**

			Study diet provided Weeks 1-6		Self-adherence to diet, food not provided Weeks 7-12	
Week	-28 to -1	0	1-5	6	7-11	12
Visit	1		2		3	
	In-Person	In-Person Or Phone	Online	In-Person	Online	In-Person
Informed Consent	X	X*				
Eligibility	X					
Medical History	X					
Diet History Questionnaire	***					X
Urine Pregnancy	X					
Randomization		X				

sCDAI (symptoms collected daily throughout study)	X***		X	X	X	X
CDAI	X			X		X
Physical Exam	X			X		X
Stool Collection	X			X		X
Fecal Calprotectin	X			X		X
Blood draw for hsCRP, HCT	X			X		X
Blood draw for plasma**	X			X		
PROMIS measures	X			X		X
Joint symptoms	X			X		X
Adverse events	X			X		X
Medications	X			X		X
One dietary recall (over the phone)	X			X		X
Satisfaction with diet			X (week 3)	X	X (week 9)	X
Weight	X			X		X
Height	X					
Vitals	X					

\*Verbal informed consent may be obtained to allow for some screening steps to begin prior to the in person visit. Written informed consent must still be obtained at the in person screening visit.

\*\*Plasma collection may not apply to all clinic sites.

\*\*\* These measures will be completed online prior to the first visit.

## 6.2 Study Intervention Phase and Follow Up Phase

### 6.2.1 Recruitment and Pre-Screening

Site Coordinators and/or Investigators will identify potential participants via review of their medical record. The Site Coordinator (SC) may contact the participant either in person or over the phone to discuss the study, complete a verbal or in-person informed consent, and ask and record pre-screening questions to determine nominal eligibility. No data will be recorded without at least verbal consent. The SC will immediately enter the pre-screening information, including the participant's contact information and mailing information, into the study data management system (DMS). The Site Coordinator will either complete the screening visit (Visit 1) at that time if the consent was done in person or will schedule a screening visit for a later date (if initial contact and consent was over the phone).

The DMS will automatically alert the Data Coordinating Center (DCC) of the new nominally eligible participant and will ship one stool collection kit to their home for the baseline stool sample collection. The database will begin automatically emailing or texting the daily sCDAI surveys to the participant.

### 6.2.2 Visit 1

The informed consent, screening, and baseline data collection which make up visit 1 can occur on the same day or be completed across several days.

At Visit 1 the Site Coordinator and/or Site Investigator must collect the following:

- Informed Consent (if not done so already)
- Medical History
- Urine Pregnancy
- Diet History Questionnaire (see below for more information)
- 24-hour dietary recall (see below for more information)
- Medications
- Joint Symptoms
- PROMIS Measures
- Physical Exam
- Vitals
- Height and weight
- Short Quality of Life in Inflammatory Bowel Disease Questionnaire (SIBDQ)
- CDAI
- sCDAI (see below for more information)
- Adverse Events
- Blood draw to measure hsCRP, hematocrit, and to collect plasma (see below for more information)
- Stool Collection (see below and section 7.8 for more information)
- Provide study instructions

sCDAI: A minimum of 5 and maximum of 7 days of patient reported symptoms will be required to compute the sCDAI to determine eligibility. The participant will accomplish this via daily online surveys sent to the participant after at least a verbal consent is obtained. The sCDAI is computed using the following equation where  $L$  is the number of liquid or very soft stools,  $A$  is the rating of abdominal pain (0-3, none to severe),  $W$  is the rating of general wellbeing (0-4, generally well to terrible),  $n$  is the day of follow-up, and  $d$  is the number of days of data used to compute the sCDAI.

$$sCDAI = 44 + \frac{7}{d} * \left( \left( 2 * \sum_{n=1}^d L \right) + \left( 5 * \sum_{n=1}^d A \right) + \left( 7 * \sum_{n=1}^d W \right) \right)$$

Stool Collection: The participant must collect a stool sample no more than 28 days from the date the participant will start the study diet and no more than 28 days after the initial form of consent. Participants at the University of Pennsylvania may bring the sample with them to visit 1. All other participants must ship the sample to the University of Pennsylvania in materials the DCC ships to the participant's home. *See section 7.8 Stool Processing for more information.*

Diet History Questionnaire (DHQ): The participant will complete an online Diet History Questionnaire at home prior or immediately following the visit in the clinic. Alternatively, the participant may complete it at their visit if a computer with internet is available. It will take approximately 30 minutes to complete. The DMS will email the participant the link to the questionnaire as well as their username and password to access the questionnaire.

24-hr Dietary Recall: A dietitian from the University of Pennsylvania will call the participant at home to ask them what they ate the day before. This should be completed on a random day between screening and the start of study diet.

FCP: Upon receipt of the stool sample, laboratory staff at the University of Pennsylvania will send a small amount of the sample to LabCorp for a baseline measurement of FCP. LabCorp will report the results to the Data Coordinating Center (Penn).

Blood draw: one tube of blood will be drawn for measuring hsCRP and one for hematocrit. Two additional tubes may be drawn for plasma collection. Blood tubes and other collection materials will be

provided to the sites. After blood is drawn, the Site Coordinator will spin the tubes of blood in a centrifuge using instructions provided from the Data Coordinating Center. They will package the spun tubes in materials provided and will place the blood sample for hsCRP and hematocrit in a LabCorp lockbox at their site. If the site does not currently have a LabCorp lockbox, LabCorp will install one. The Site Coordinator must contact LabCorp to inform them there is a sample for them to pick up. A LabCorp driver will pick up the sample. The blood samples for plasma will be stored at the site in a -80° C freezer and shipped in batch to Biostorage at the end of the study. See the Manual of Procedures for processing instructions for plasma.

Steroid Equivalency chart:

Cortisone	25mg
Hydrocortisone	20mg
Prednisone or Prednisolone	5mg
Methyl prednisolone	4mg
Dexamethasone	0.75mg

Randomization will occur after eligibility is confirmed and a stool sample is received.

To determine the participant's randomization, the Site Coordinator must first confirm receipt of the stool sample at Penn and then confirm the participant's eligibility based on Visit 1 data collection and document both in the Data Management System (DMS). Upon documentation of both in the DMS, the DMS will automatically provide the Site Coordinator with the participant's randomization.

The Site Coordinator will inform the participant of their randomized diet in person or over the phone.

The DCC will be alerted to the participant's eligibility and randomization, after which they will ship two more stool collection kits to the participant's home for the remainder of the study.

### **6.2.3 Visit 2 (week 6 visit)**

The following will be conducted at Visit 2 (week 6):

- 24-hour dietary recall (see below for more info)
- Medications
- Joint Symptoms
- PROMIS Measures
- Physical Exam
- Weight
- CDAI
- SIBDQ
- sCDAI (same as for visit 1)
- Adverse Events
- Blood draw to measure hsCRP, hematocrit, and to collect plasma
- Stool Collection
- Online Diet Satisfaction Survey (completed at home)

FCP: same as for visit 1

24-hr Dietary Recall: A dietitian from the University of Pennsylvania will call the participant at home to ask them what they ate the day before. This should be completed on a random day during week 6.

Blood draw: Blood draw: one tube of blood will be drawn for measuring hsCRP and one drawn for hematocrit. One additional tube may be drawn for plasma. The samples will be processed in the same manner as in Visit 1.

Stool collection: participants must collect one stool sample during days 38-40.

Recommended Steroid Taper after week 6: participants who are on steroids may taper after week 6. The following tapering schedule is to be used but can be modified by the treating physician in response to symptoms or in the case of special circumstances (e.g. a slower taper may be used for patients with a history of long-term steroid use):

20mg/day for one week → 15mg/day for one week → 10 mg/day for one week → 5 mg/day for one week → 2.5 mg/day for one week → off

#### **6.2.4 Visit 3 (week 12 visit)**

The following will be conducted at Visit 3 (week 12):

- Diet History Questionnaire (same as for visit 1)
- 24-hour dietary recall (see below for more info)
- Medications
- Joint Symptoms
- PROMIS Measures
- Physical Exam
- Weight
- CDAI
- SIBDQ
- sCDAI (same as for visit 1)
- Adverse Events
- Blood draw to measure hsCRP and hematocrit Stool Collection
- Online Diet Satisfaction Survey (completed at home)

FCP: same as for visit 1

24-hr Dietary Recall: A dietitian from the University of Pennsylvania will call the participant at home to ask them what they ate the day before. This should be completed on a random day during week 12.

Stool Collection: participants must collect one stool sample during days 80-82.

#### **6.2.5 End of Study Visit**

The end of study visit will take place at week 12 or at the visit where the participant withdraws or is withdrawn from the study. This visit will include a physical exam to obtain CDAI score. An sCDAI score will also be calculated. Participants will be asked to collect a stool sample at home and ship it to Penn. Stool will be shipped from Penn to LabCorp to obtain an FCP result. Participants will be asked to complete a DHQ, SIBDQ, a 24-hour dietary recall, and provide information about adverse events, medications, joint symptoms and provide health status information (physical, mental and social) to obtain a PROMIS score. Participants will also be weighed and have their blood drawn to measure hsCRP and hematocrit.

### **6.3 Rescue Therapy [if applicable]**

Participants will remain under the care of their treating gastroenterologist while in the study. If their symptoms worsen, participants will contact their treating gastroenterologist and follow any recommendations with regard to changes in therapy for their Crohn's disease. Participants whose worsening symptoms require a change in the current treatment for Crohn's disease will be considered study treatment failures and will be withdrawn from the study. See Section 6.5 for subject withdrawal information.

### **6.4 Unscheduled Visits**

Unscheduled visits could potentially occur if a participant experiences an Adverse Event that requires medical evaluation.

## **6.5 Subject Withdrawal**

Participants may withdraw from the study at any time.

Participants may be withdrawn at the discretion of the investigator prior to randomization for the following reasons:

- Failure to provide the baseline stool sample
- Failure to complete at least 5 of the 7 baseline sCDAI surveys

Participants will be withdrawn from the study if they experience worsening symptoms requiring a change in their Crohn's disease treatment, the initiation of an antibiotic for gastrointestinal symptoms, and/or an increase of greater than 10mg/day of prednisone or equivalent for a non-gastrointestinal condition\*.

*\*Please see section 6.2.2 for equivalency chart*

Participants who have been randomized to one of the two diets and withdraw early from the study should complete an end of study visit and provide a stool sample at the time of withdrawal as described in section 6.2.5.

If the participant wishes to discontinue the study diet early for reasons not related to worsening Crohn's Disease (e.g., they don't like the diet), they will be asked to remain in follow-up and complete the next in-person visit at the target date of that visit (either week 6 or week 12). This will be the end of study visit.

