On Day 84 (+ or – 3 days), participants will come into the clinic for a visit that will involve: collection of information about their symptoms which will be used to obtain an sCDAI score, a physical exam to obtain CDAI score, one tube of blood drawn to measure hsCRP and one for HCT, providing information about adverse events, medications, joint symptoms, providing health status information (physical, mental and social) to obtain a PROMIS score and being weighed. Participants will take a satisfaction survey about the study diet online and they will complete a Diet History Questionnaire online.. The participant will collect one stool sample during days 80-82 and ship it to [name] lab at the University of Pennsylvania. On a randomly selected day during week 12, a dietitian will contact participants by phone to ask them about what they ate on the previous day. Participants complete the study at the end of the week 12 visit.

Site Coordinators may call participants as needed to remind them of their upcoming study visits, sample collections, and online surveys.

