#### **8.5 Subject Population(s) for Analysis**

As a comparative effectiveness study, the primary efficacy and safety analysis will use the principle of intention to treat such that all randomized patients will be included in the group that they were randomized to, regardless of the level of adherence with the assigned diet.

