Reports on form completion, missing data reports so that we are aware of patterns of missing data early on in the study, logic checks will be completed throughout the study. Reminders will be automatically sent to the sites from the DMS for upcoming visit target dates 14 days prior to the visit target date. Another reminder will be sent in advance of visit window closing dates. Not only are we going to check for missing data we are going to proactively manage the data to avoid missing data.

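### Section 6.5 asks early diet stoppers to stay in follow-up only if the reason is unrelated to worsening Crohn's disease; symptom-driven stoppers with no withdrawal-triggering medication change get no such request

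*Combined protocol and SAP*

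**What the plan says.** Protocol section 6.5 has three rules for randomised participants.

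- **Withdrawal by rule.** "Participants will be withdrawn from the study if they experience worsening symptoms requiring a change in their" Crohn's treatment. A new antibiotic for gastrointestinal symptoms, or a prednisone rise of more than 10 mg/day for a non-gastrointestinal condition, has the same effect. Section 6.3 adds that those whose worsening needs a treatment change "will be considered study treatment failures and will be withdrawn from the study".
- **Early withdrawal from the study.** These participants "should complete an end of study visit and provide a stool sample at the time of withdrawal". Section 6.2.5 agrees: the end of study visit is at week 12 or "at the visit where the participant withdraws or is withdrawn from the study".
- **Stopping the diet only.** "If the participant wishes to discontinue the study diet early for reasons not related to worsening" Crohn's disease, the participant is asked to remain in follow-up to the target date of the next in-person visit, week 6 or week 12. A closing sentence makes that visit the end of the study for this person.

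The analysis includes everyone in the assigned arm "regardless of the level of adherence with the assigned diet" (section 8.5). Withdrawal or loss before week 6 is a failure on the primary outcome (sections 3.4.1.1 and 8.4.2; Appendix G, 5.5.2). Missing continuous secondary outcomes are filled by BOCF, with last observation carried forward (LOCF) or multiple imputation as sensitivity analyses. The within-arm change tests use a worst-case rule instead.

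**The concern.** A participant who stops the diet because symptoms are worse, but has no treatment change, gastrointestinal antibiotic or steroid increase, meets no withdrawal trigger and is also outside the request to stay. Section 8.4.2 and Appendix G, 5.5.2 both expect missing follow-up to be more common among participants whose symptoms worsened, so the request leaves out the group the plan itself worries about. The main retention incentive in section 8.4.2, free food in return for data, has no hold on someone who no longer wants the diet.

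The trial is open label. Whether a stop is recorded as worsening or as dislike could therefore differ between arms, and with it who is asked to stay. At stake are observed week-6 and week-12 values whose absence depends on the reason for stopping.

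**Working it through.** **1. Reading the rules together.**

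| Situation | What the protocol asks |
|---|---|
| Worsening with treatment change or other medication trigger | Withdrawal; visit at that time (6.3, 6.5) |
| Leaves the study for any reason | Visit at time of withdrawal (6.2.5, 6.5) |
| Stops diet, reason unrelated to worsening | Stay to next target-date visit, then end of study (6.5) |
| Stops diet because of symptoms, no medication trigger | No specific instruction; general schedule only (3.2.3) |

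Sections 6.2.5 and 6.3 and Appendix G do not fill the last row.

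**2. The plan's own figure.** Appendix G, 5.2 gives 97 per arm and 80% power for 40% versus 60%, two-sided 5%. Normal approximation: Φ[(0.20 − 1.96·√(2·0.5·0.5/97)) / √((0.4·0.6 + 0.6·0.4)/97)] = Φ[(0.20 − 0.1407)/0.0703] = 0.800, so it reproduces. Exact enumeration of the unstratified chi-square test gives 80.7% power and 4.9% type I error. These are the reference values below.

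**3. Primary outcome.** The documents give no rate of symptom-driven stopping, so every rate here is an assumption.

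- s = share of an arm that stops for symptoms without a trigger: 5% to 15%
- r = share of those who would have sCDAI below 150 at week 6: 10% to 30%
- w1, w2 = share of them, in the two arms, labelled as worsening who then leave

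Only would-be remitters who leave are reclassified, so each arm's rate falls by s·r·w and the between-arm shift is s·r·(w1 − w2). If w1 = w2, the shift is 0.

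| s | r | Split w1/w2 | Shift (points) | Type I error | Power, shift against / for SCD |
|---|---|---|---|---|---|
| 5% | 10% | 60/40 | 0.05·0.10·0.20 = 0.10 | 4.89% | 80.3% / 81.1% |
| 15% | 30% | 60/40 | 0.15·0.30·0.20 = 0.90 | 5.09% | 77.0% / 84.0% |
| 5% | 10% | 75/25 | 0.05·0.10·0.50 = 0.25 | 4.90% | 79.7% / 81.6% |
| 15% | 10% | 75/25 | 0.15·0.10·0.50 = 0.75 | 5.01% | 77.6% / 83.5% |
| 15% | 30% | 75/25 | 0.15·0.30·0.50 = 2.25 | 6.09% | 70.7% / 88.3% |

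The last row needs every rate at its extreme.

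**4. Continuous secondary outcomes.** If half of these stoppers leave, the observed week-6 values lost per arm are 97·0.05·0.5 = 2.4 to 97·0.15·0.5 = 7.3. The same people would also miss week 12.

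For PROMIS, suppose leavers had truly worsened by 5 T-score points (half the SD of 10). BOCF records no change, so the between-arm mean shifts by s·(w1 − w2)·5:

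- 60/40 split: 0.05·0.20·5 = 0.05 to 0.15·0.20·5 = 0.15
- 75/25 split: 0.05·0.50·5 = 0.125 to 0.15·0.50·5 = 0.375

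The shift flatters whichever arm loses more worsened participants.

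**The case against.** The strongest reply is that nothing removes these participants. One who stops the diet without leaving the study stays on the general schedule of daily surveys and visits at days 42 and 84. None of this depends on eating the diet. "Site Coordinators may call participants as needed to remind them of their upcoming study visits" (section 3.2.3), and "Reminders will be automatically sent to the sites from the DMS for upcoming visit target dates" (Appendix C, section 5). The section 6.5 request also shortens follow-up, because someone who dislikes the diet and stops before week 6 finishes at week 6. Read literally, the symptom-driven stopper is scheduled for more follow-up, not less.

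This stands as a reading of the text. It rules out an inference a reader might draw, that the protocol orders these participants out or leaves them unobserved. It does not settle what a site will do. The protocol treats diet stopping as needing an explicit request, limits that request by reason, and offers a visit-at-exit route for those who leave.

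Three further replies also have force:

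- The group is narrow. Section 6.3 sends worsening patients to their gastroenterologist, and those whose treatment changes are withdrawn and scored as failures.
- The withdrawal visit collects sCDAI, CDAI, stool, PROMIS and bloods, and LOCF could carry a worsened score forward from it.
- Results are to be interpreted in the light of the sensitivity analyses, so as not to favour SCD.

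These soften the BOCF point without removing it. The withdrawal visit is not at week 6, it has to take place to help, and BOCF remains the main method.

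**Conclusion.** The point holds as a minor one. The explicit retention request depends on the reason for stopping, and no other section extends it to symptom-driven stoppers without a medication trigger.

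A reader might infer that the primary comparison is biased or its type I error inflated. The documents do not support that. The outcome is defined either way: observed sCDAI for those who stay, failure for those who leave before week 6. The shift is zero with equal labelling and below one percentage point in the moderate cases. Its direction is unknown, and all the rates are assumed. The 6.1% type I error arises only at the extreme corner. It requires 30% of people who stopped because of symptoms to be in remission by week 6.

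What remains is avoidable loss of observed week-6 and week-12 values, related to the reason for stopping. For a participant still worse at the visit, BOCF is not conservative, because it substitutes the better baseline score. On the assumed rates the PROMIS effect is also small, at most about 0.4 points against an SD of 10.

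**What to change.** In the last paragraph of section 6.5, make two deletions: the condition on the reason for stopping, and the closing sentence that makes the next visit the end of the study. Both are needed. Removing only the condition would bring symptom-driven stoppers under a rule that ends follow-up at week 6 and would cost their week-12 data.

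In their place, ask every randomised participant who stops the diet without a withdrawal-triggering medication change to continue the daily surveys and attend all remaining scheduled visits, week 6 and week 12. Record the reason for stopping as descriptive data. Leave the scoring rules as they are: therapy change, withdrawal or loss before week 6 is a failure; otherwise use the observed sCDAI.

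The cost is small. The surveys are automated, the visits are already in the schedule, and the sample size does not change. There will be a few more visits, and some off-diet participants may be scored as in remission. That can already happen to those who stop because they dislike the diet, and it is consistent with analysis by assigned arm.
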